## 3. STUDY PLAN

### 3.1 Overall Design

This Phase 2 study will be an interventional, open-label, single arm trial where each patient is his/her own “intrapatient” control. All patients will receive a single mg/kg dose of pgsitacianine prior to standard of care surgery.

Patients will have a biopsy confirmed diagnosis, or a high clinical suspicion of a lung malignancy based on MRI, CT and/or PET imaging. A total of up to 40 patients will be enrolled in this trial. Enrollment will be open first to Part 1 with the opportunity to open Part 2 for enrollment following the demonstration of satisfactory pgsitacianine sensitivity and specificity values of 70% or greater in Part 1. The sponsor reserves the right to perform an interim analysis following early enrollment (i.e.,  $n \leq 10$  patients) to determine the feasibility and benefit of pgsitacianine as an adjunct to standard of care surgical resection of lung malignancies. Interim analysis will assess the utility of pgsitacianine based on mean fluorescence intensity analysis, calculation of tumor to background ratios, calculation of sensitivity and specificity, safety, and investigator feedback.

The surgeon will begin by attempting to perform their SOC tumor resection. If the tumor is unable to be located under standard white light conditions, an appropriate FDA-cleared near-infrared imaging device (Examples found in [Appendix 2: FDA-Cleared NIR Imaging Devices](#)) may be used to aid in the location of the primary tumor. Localization of the primary tumor, when unable to be located using white light imaging, in conjunction with pathology confirmed presence of disease will be considered a clinically significant event.

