3. STUDY DESCRIPTION

3.1 Study Design

This Phase 2 study will be an interventional, open-label, single arm trial where each patient is his/her own “intrapatient” control. All patients will receive a single █ mg/kg dose of pegsitacianine administered █ prior to standard of care (SOC) surgery. The study will be conducted in two Parts. Part 1 will enroll patients undergoing minimally invasive procedures (i.e., video-assisted thorascopic surgery [VATS] or robotic surgery). Part 2 will be opened at the discretion of the Sponsor and include patients undergoing open thoracotomy for the removal of their disease. [Note: Part 2 was not opened to enrollment.]

Patients will have a biopsy confirmed diagnosis, or a high clinical suspicion of a lung malignancy based on CT and/or PET imaging. A total of up to 40 patients will be enrolled in this trial. The sponsor reserves the right to perform an interim analysis following early enrollment (n ≤ 10 subjects) to determine the feasibility and benefit of pegsitacianine as an adjunct to SOC surgery.

The surgeon will attempt to perform their SOC resection of visible tumors. If the tumor is unable to be located under standard white light conditions, an appropriate near-infrared (NIR) imaging device may be used to aid in the location of the primary tumor. Localization of the primary tumor using NIR imaging in conjunction with pathology confirmed presence of disease will be considered a clinically significant event.

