5. ANALYSIS ENDPOINTS

5.1 Efficacy Endpoints

5.1.1 Clinically Significant Event Endpoints

Performance metrics will include the identification of a CSE detected by pegasitacianine. CSEs will include pegasitacianine detection of primary tumors otherwise undetectable using SOC procedures, detection of occult disease not otherwise known by the surgeon to exist (as synchronous disease), the detection of a positive surgical margin, and accurate identification of tumor negative SOC biopsies. A list of CSEs and their definitions is provided below.

- **Detection of Synchronous Disease** – identification of tumor-containing tissue due to pegasitacianine fluorescence, confirmed via histopathological analysis, that otherwise went undetected during pre-operative imaging (PET, CT, MRI) or by the surgeon during SOC surgery.
 - This occurs when a specimen that comes from the thoracic cavity or lymph nodes, is (1) collected via fluorescence and (2) is pathologically-confirmed as a tumor. Note that any specimen collected from the thoracic cavity following SOC will be considered to be collected by fluorescence.

- Detection of Positive Surgical Margin – following the completion of SOC surgery, the surgical fields will be examined for residual fluorescence. Detection of a positive surgical margin would be those specimens collected as a result of residual pegsitacianine fluorescence following the completion of SOC surgery that return a histologically positive for tumor outcome.
 - This occurs when a margin specimen (either from the primary tumor or a lung resection margin) (1) is collected via fluorescence and (2) is pathologically-confirmed as a tumor. Note that any lung resection margin collected will be considered to be collected by fluorescence.
- Identification/Localization of the Primary Tumor – during SOC surgery, the surgeon will examine the affected lung to locate the primary tumor. If the primary tumor is not visually apparent using standard imaging methods the surgeon may use the NIR imaging device to aid in localization. If the NIR imaging identifies and/or locates the primary tumor, which was undetectable using SOC approaches, this will be deemed a CSE.
 - This occurs when the primary tumor is not located using SOC approaches, and is instead identified using NIR imaging.

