- Tumor Negative SOC Biopsies – during SOC surgery, the surgeon will collect tissue specimens that are suspicious for disease. If those samples do not demonstrate pegsitacianine fluorescence and are found to be devoid of tumor pathologically, those specimens would be included as a tumor negative SOC biopsy.
 - This occurs when any SOC sample (primary tumor, additional SOC specimen, or lymph node) that is collected that is found to be negative for tumor, and did not fluoresce during *ex situ* imaging.

A subject with any CSE will be considered a CSE responder.

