5.1.2 Diagnostic Imaging Endpoints

Diagnostic performance of pegsitacianine will be assessed by calculating sensitivity, specificity, NPV, and PPV of pegsitacianine in detecting tumor containing tissue. The *ex situ* fluorescence status (any fluorescence vs. no fluorescence) of collected SOC and pegsitacianine guided specimens, as well as lymph nodes, will be compared to histological analyses of the collected specimens. Sensitivity and specificity for detecting tumor-containing tissue versus normal tissue

will be evaluated using tissue specimen fluorescence and the corresponding pathological outcomes.

True/false/negative/positive definitions are as follows:

- False positive is defined as fluorescence was observed on the sample but the sample was not found to have tumor via pathology.
- False negative is defined as no fluorescence was observed on the sample but the sample was found to have tumor via pathology.
- True positive is defined as fluorescence was observed on the sample and the sample was found to have tumor via pathology
- True negative is defined as no fluorescence was observed on the sample and the sample was found not to have tumor via pathology.

Pegsitaricaine sensitivity and PPV will be calculated using the following equations:

$$\text{Sensitivity} = \frac{\text{\# of True Positive Specimens}}{\text{\# of True Positive Specimens} + \text{\# of False Negative Specimens}}$$

$$PPV = \frac{\# \text{ of True Positive Specimens}}{\# \text{ of True Positive Specimens} + \# \text{ of False Positive Specimens}}$$

Pegsiraniline specificity values and NPV will be calculated using the following equations:

$$\text{Specificity} = \frac{\text{\# of True Negative Specimens}}{\text{\# of True Negative Specimens} + \text{\# of False Positive Specimens}}$$

$$NPV = \frac{\# \text{ of True Negative Specimens}}{\# \text{ of True Negative Specimens} + \# \text{ of False Negative Specimens}}$$

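### The SAP defines the primary-tumor localization CSE in two ways: Section 3.1 attaches pathology confirmation, Section 5.1.1 does not

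*SAP*

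**What the plan says.** SAP 5.1.1 lists four CSE types, each with a description and a short operational rule. For localization of the primary tumor the rule is "This occurs when the primary tumor is not located using SOC approaches, and is instead identified using NIR imaging". The description above it also makes NIR identification sufficient. Protocol 9.3 carries the same rule.

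SAP 3.1 puts it differently: "Localization of the primary tumor using NIR imaging in conjunction with pathology confirmed presence of disease will be considered a clinically significant event". The Protocol Summary agrees, and Protocol 3.1 likewise credits localization "in conjunction with pathology confirmed presence of disease will be considered a clinically significant event".

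The other detection rules in SAP 5.1.1 state the condition outright. A margin specimen counts when it "1) is collected via fluorescence and (2) is pathologically-confirmed as a tumor", and the synchronous-disease rule has the same two parts. The tumor-negative biopsy rule also depends on a pathology result.

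The responder rule is "A subject with any CSE will be considered a CSE responder". SAP 7.10.1.1 reports responders, and subjects with each CSE type, with Clopper-Pearson 95% intervals.

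**The concern.** Two analysts working from the same SAP could classify the same subject differently for the primary endpoint. The case that separates them is a target lesion that standard approaches miss, NIR imaging finds, and pathology shows to be benign.

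The term primary tumor does not close the gap. Entry does not require a tissue diagnosis: "Patients will have a biopsy confirmed diagnosis, or a high clinical suspicion of a lung malignancy based on CT and/or PET imaging". The SAP itself also uses the term for a lesion that may turn out benign, since the tumor-negative biopsy rule covers "any SOC sample (primary tumor, additional SOC specimen, or lymph node) that is collected that is found to be negative for tumor".

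Section 5.1.1 is the endpoint definition a programmer would naturally follow, so the looser rule is the more likely one to be applied. Omitting the condition can only add responders, so any error is upward. Protocol 9.1 says the study is meant to inform power calculations for later studies, so an unclear responder definition could carry forward.

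**Working it through.** **Step 1. Compare the definitions.** The plan has no figure to reproduce: the sample size rests on historical experience, with no alpha, power or target precision.

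| CSE type | Pathology condition in SAP 5.1.1 | Pathology condition elsewhere |
|---|---|---|
| Synchronous disease | Yes, tumor confirmed | – |
| Positive margin | Yes, tumor confirmed | – |
| Tumor-negative SOC biopsy | Yes, tumor absent | – |
| Primary-tumor localization | **None** | SAP 3.1, Protocol Summary and Protocol 3.1: yes; Protocol 9.3: none |

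Localization is the only type in 5.1.1 without a pathology criterion. The precedence clause in SAP 1 ranks the SAP above the protocol. It does not help when both definitions are in the SAP. SAP 8 plans no deviations.

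**Step 2. Classify a primary that standard approaches missed and NIR found.** SAP 3.1 is read here as a requirement.

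| Pathology | Ex situ fluorescence | Localization CSE, 5.1.1 | Localization CSE, 3.1 | Specimen class, 5.1.2 |
|---|---|---|---|---|
| Tumor | Yes | Yes | Yes | True positive |
| Tumor | No | Yes | Yes | False negative |
| Benign | Yes | **Yes** | **No** | False positive |
| Benign | No | **Yes** | **No**, but may count as a tumor-negative SOC biopsy | True negative |

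The third row matters most. SAP 5.1.2 says "False positive is defined as fluorescence was observed on the sample but the sample was not found to have tumor via pathology", so that specimen is a primary-endpoint success and a secondary-endpoint error. The tumor-negative biopsy rule cannot also capture it, because that rule requires no ex situ fluorescence.

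**Step 3. Effect on the localization rate.** Inputs are N=40 (SAP 4) and Clopper-Pearson 95% intervals (SAP 7.10.1.1). The event counts are assumed.

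- 0/40 = 0% (0–8.8%) becomes 1/40 = 2.5% (0.1–13.2%).
- 3/40 = 7.5% (1.6–20.4%) becomes 4/40 = 10.0% (2.8–23.7%).

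If a fraction b of NIR-localized primaries is benign, the ratio of the looser to the stricter rate is 1/(1−b). For assumed b of 10%, 20% and 30%:

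- 1/0.90 = 1.11
- 1/0.80 = 1.25
- 1/0.70 = 1.43

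**Step 4. Effect on the any-CSE rate.** An affected subject with no other CSE adds 1/N: 1/40 = 2.5 points, or 1/30 = 3.3 points with an assumed 30 evaluable subjects. With an assumed 12/40 responders under the stricter rule (30.0%, 16.6–46.5%), adding such subjects gives:

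- one: 13/40 = 32.5% (18.6–49.1%)
- two: 14/40 = 35.0% (20.6–51.7%)
- three: 15/40 = 37.5% (22.7–54.2%)

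These are upper bounds, because one tumor-free, non-fluorescent SOC lymph node already makes a subject a responder. Suppose the subject has m tumor-free SOC nodes, each independently non-fluorescent with probability p. The chance of no CSE from the nodes is (1−p)^m, so the expected gain is (1−p)^m / N. The value p=0.70 is borrowed from the specificity threshold for opening Part 2, and p=0.50 is a second assumption.

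| m | Gain at N=40, p=0.70 | Gain at N=40, p=0.50 |
|---|---|---|
| 0 | 1/40 = 2.5 points | 2.5 points |
| 1 | 0.30/40 = 0.75 | 0.50/40 = 1.25 |
| 2 | 0.09/40 = 0.23 | 0.25/40 = 0.63 |
| 3 | 0.027/40 = 0.07 | 0.125/40 = 0.31 |

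**The case against.** **The sections can be read together.** Section 5.1.1 is silent on pathology and does not say confirmation is unnecessary, so 3.1 could supply it. SAP Table 1 speaks of detecting disease, which a benign nodule arguably is not. This reading is possible, but the explicit conditions in the neighboring rules and the SAP's own mention of a tumor-negative primary weaken it. If it is what the sponsor intends, it leads to the same added clause.

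**The two endpoints measure different things.** Subject-level help in finding a target is not specimen-level agreement with histology, so different outcomes for one specimen are not in themselves a contradiction. That is fair. The contradiction is between 3.1 and 5.1.1, and the false-positive overlap shows only where it matters.

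**The effect is small and rests on assumptions.** This largely stands. The benign fractions have no source in the documents. The node calculation assumes independence, although SAP 7.10.3.2 raises within-subject correlation. A subject whose benign nodule fluoresced may well have fluorescent nodes too, so the small gains could be too small. Additional SOC specimens, which the calculation leaves out, work the other way. Only the ceilings of 2.5 points at N=40 and 3.3 at N=30 are secure. No hypothesis test is planned, and the listings would allow recalculation.

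**SAP 7.1 calls for a protocol amendment when a method change may affect the primary conclusions.** It also allows SAP updates before database lock. The change here aligns the SAP with a condition already in Protocol 3.1 and affects no test or threshold, so an amendment for this point alone does not appear necessary.

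**Conclusion.** The concern holds. As written, SAP 5.1.1 would count a benign, fluorescent, NIR-localized nodule as a primary-endpoint success, while SAP 3.1 and Protocol 3.1 tie that credit to confirmed disease. Nothing in the SAP says which text governs.

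The separately reported localization rate takes the full effect: 2.5 points per benign localization at N=40. On the any-CSE rate that figure is a ceiling, reached only when the subject has no other CSE. How often this would happen is unknown. The direction is not: the looser rule can only raise the rate. This is a definition to settle before lock, and it does not threaten a formal conclusion.

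**What to change.** Before database lock, extend the localization rule in SAP 5.1.1 so that the lesion found by NIR imaging must also be confirmed as tumor on pathology. This matches SAP 3.1 and Protocol 3.1. Record in SAP 8 that the definition follows Protocol 3.1 and not the shorter wording in Protocol 9.3. Align Protocol 9.3 if the protocol is amended for another reason.

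The cost is one clause and one line. SAP 7.10.2.1 already lists pathology by subject and specimen, so no new data are needed, and the sponsor has already written the condition elsewhere. The downside is a possibly slightly lower CSE rate. Settling it before lock also avoids choosing between the definitions once results are known.

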- Tumor Negative SOC Biopsies – during SOC surgery, the surgeon will collect tissue specimens that are suspicious for disease. If those samples do not demonstrate pegsitacianine fluorescence and are found to be devoid of tumor pathologically, those specimens would be included as a tumor negative SOC biopsy.
  - This occurs when any SOC sample (primary tumor, additional SOC specimen, or lymph node) that is collected is found to be negative for tumor, and did not fluoresce during *ex situ* imaging.

The number and proportion (with corresponding two-sided exact 95% confidence intervals) of subjects with any CSE will be reported.

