7.9.5 Surgery Details and Specimen Collection

Surgery details including the following will be summarized on a patient level using descriptive statistics in the Safety population:

- Duration of surgery
- Location of tumor

- Method of tumor localization, including number of subjects with primary tumor(s) identified using NIR imaging
- Number of SOC specimens collected
- Number of additional lung nodules/areas found as a result of NIR imaging following SOC procedures and confirmed to be cancer
- Number of SOC specimens collected, found to be negative for tumor, and did not fluoresce during *ex situ* imaging
- Number of areas with fluorescence removed on:
 - Lung resection margins
 - Thoracic cavity
 - Lymph nodes
 - Total (any area)
- Number of areas with fluorescence on lung resection margins
- Subjects with fluorescence observed anywhere in thoracic cavity
- Number of lymph nodes collected as SOC surgery
- Time spent imaging
- Camera system used

A listing will also be generated.

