7.10.1 Primary Analyses

7.10.1.1 Analysis of Clinically Significant Events

The number and proportion of subjects with CSEs will be summarized by Part and overall. CSE responders will be summarized, as well as subjects with each type of CSE. These summaries will include 95% 2-sided confidence intervals for the proportion of CSEs calculated via Clopper-Pearson method.

A listing of all CSEs by patient will be provided.

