7.10.2 Secondary Analyses

7.10.2.1 Analysis of Diagnostic Imaging

The positive predictive value, negative predictive value, sensitivity, and specificity (specimen level) will be calculated and summarized for each Part and overall. The summary will include the true/false negative/positive rate and number of specimens. Two-sided 95% confidence intervals will be calculated for each rate via Clopper-Pearson method.

A listing by subject and specimen showing the specimen type (primary tumor/ additional SOC specimen, lung resection margin, thoracic cavity, lymph node), attainment by SOC or fluorescence (if primary/ additional SOC/ lymph), pathology result, fluorescence *in situ* and *ex situ*, and fluorescence measures (MFI and TBR) will be provided.

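### The primary CSE definition does not settle whether a near-infrared-localized primary needs pathology confirmation, and no combined rate over the three tumor-finding event types is planned

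*SAP*

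**What the plan says.** **Event types and responder rule.** SAP 5.1.1 and Protocol 9.3 define four CSE types: synchronous disease, positive surgical margin, localization of the primary tumor, and tumor-negative SOC biopsy. The SAP then states: "A subject with any CSE will be considered a CSE responder".

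**Tumor-negative type.** In the SAP it is met by "any SOC sample (primary tumor, additional SOC specimen, or lymph node) that is collected that is found to be negative for tumor" and without ex situ fluorescence. Protocol 9.3 has the same rule, for "any SOC sample (primary tumor, additional SOC specimen, or lymph node) that is collected is found to be negative for tumor". Neither sets a minimum number of specimens.

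**Localization type.** SAP 5.1.1 and Protocol 9.3 ask only that SOC approaches failed to locate the primary and that NIR imaging identified it. SAP 3.1, the Protocol Summary (Trial Design) and Protocol 3.1 add that pathology must confirm disease.

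**Planned outputs.** SAP 7.10.1.1 says that "CSE responders will be summarized, as well as subjects with each type of CSE", with two-sided 95% Clopper-Pearson intervals, and that "A listing of all CSEs by patient will be provided". SAP 7.9.5 adds related counts, such as "Number of SOC specimens collected, found to be negative for tumor, and did not fluoresce during" ex situ imaging. The specimen listing in SAP 7.10.2.1 includes "attainment by SOC or fluorescence (if primary/ additional SOC/ lymph), pathology result", and fluorescence in situ and ex situ.

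**Status of the rate.** Protocol 9.1 says the study is not powered for hypothesis testing and is meant to inform power calculations for later studies. No target CSE rate is given.

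**The concern.** A primary endpoint should give one count from one dataset. Here two programmers working from different sections of the same SAP could count NIR-localized primaries differently.

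The any-CSE rate also pools two different things: tumor that the agent helped to find, and benign tissue that stayed dark. Someone asking in how many patients the agent found disease that SOC missed cannot read the answer from the any-CSE rate, and no other planned row gives it. They would have to rebuild it from a listing, without a planned interval and with the localization rule unsettled.

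**Working it through.** The plan has no figure to reproduce: the sample size of 40 is given without a target rate, precision or power. The check is therefore a comparison of texts, followed by arithmetic on what the planned rows can and cannot show.

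**Step 1. The localization rule.** Protocol 5.1 admits patients on high clinical suspicion from imaging, without biopsy, so some nodules may prove benign. Take a benign nodule that SOC approaches could not locate and NIR did:

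| Ex situ status | Localization CSE, SAP 5.1.1 | Localization CSE, SAP 3.1 | Class in SAP 5.1.2 | Tumor-negative CSE |
|---|---|---|---|---|
| Fluorescent | Yes | No | False positive | No |
| Dark | Yes | No | True negative | Yes, if classed as an SOC sample |

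The localization row differs between the two texts in both cases. The responder count differs in the fluorescent case, if the subject has no other CSE. It also differs in the dark case if the specimen is not classed as SOC and there is no other CSE. In the fluorescent case, one specimen is an event in favor of the agent in the primary analysis and an error of the agent in the secondary one. SAP section 1 lets the SAP overrule the protocol, but both readings stand in the SAP, so that rule does not decide.

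**Step 2. What the by-type rows say about the missing rate.** A subject can have several types. With counts x1, x2, x3 of n subjects for the three tumor-finding types, the number with at least one lies between max(x1, x2, x3) and min(n, x1 + x2 + x3). For hypothetical counts of 2, 2 and 2 of 40:

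- lower bound: 2/40 = 5.0%, Clopper-Pearson 95% CI 0.6-16.9%
- upper bound: 6/40 = 15.0%, 95% CI 5.7-29.8%

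Here n = 40 is the planned maximum; the Efficacy population may be smaller.

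**Step 3. What the any-CSE rate shows alone.** An agent that never fluoresced would make a responder of every subject with at least one tumor-negative SOC specimen. If 90% of subjects had one (an assumption), the any-CSE rate would be 36/40 (95% CI 76.3-97.2%) with no tumor found.

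**Step 4. How much the tumor-negative type can contribute.** The documents give neither the number of SOC specimens per subject nor their tumor-negative share, so this is illustration only. Let s be the share of subjects with m non-primary SOC specimens, q the tumor-negative share of those, and spec the specimen specificity. Take a tumor-finding rate t = 0.15, independent of the rest. Then

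d = s × (1 − (1 − q × spec)^m), and any-CSE rate = 1 − (1 − t)(1 − d).

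| Case | s | m | q | spec | d | Any-CSE rate |
|---|---|---|---|---|---|---|
| Low | 0.5 | 1 | 0.3 | 0.75 | 0.5 × 0.225 = 11.3% | 24.6% |
| Middle | 0.8 | 2 | 0.5 | 0.75 | 0.8 × (1 − 0.625²) = 48.8% | 56.4% |
| High | 1 | 3 | 0.8 | 0.90 | 1 − 0.28³ = 97.8% | 98.1% |

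With a within-subject correlation of 0.5 (beta-binomial), the high case gives d = 86.4% and an any-CSE rate of 88.4%. The specificity of 75% is reported in Protocol 1.2 for ON-1001, which Protocol 4.3 shows enrolled other tumor types. The 0.90 and all other inputs are assumptions. With tumor finding fixed at 15%, the any-CSE rate runs from about 25% to 98%.

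**The case against.** **The composite is declared.** Tumor-negative SOC biopsies are listed in the objectives and endpoints of both documents. This stands: the type is there by design, and nothing here asks for its removal.

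**The results are separated.** A reader might infer that benign specimens hide the detection results. The documents do not support that. Each type has its own exact interval, CSEs are listed by patient, and with at most 40 subjects the combined count can be made from the listing. What remains is that this count is not planned and has no planned interval.

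**Nothing stated turns on the rate.** There is no test. Opening Part 2 rests on sensitivity and specificity of at least 70%. The interim criteria in Protocol 9.8 do not name the CSE rate, although the decision is described as a synthesis of all available information. This stands and limits the second part to interpretation.

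**SAP 3.1 supplies the missing condition, and the definition speaks of the primary tumor.** Reading the sections together is sensible and may be what was meant. But the tumor-negative rule lists the primary tumor among samples that may prove negative, so the term is a specimen label, not a confirmed diagnosis.

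**Other wording.** A reader might infer that the notes deeming every lung resection margin and post-SOC cavity specimen to be collected by fluorescence credit the agent with dark tissue. In SAP 3.1, lung-margin excision imaging and cavity resection follow observed fluorescence, so that reading is strained. A reader might also set "the surgeon will collect tissue specimens that are suspicious for disease" against the broader rule for any SOC sample and conclude that the tumor-finding rate is affected. It is not: that wording concerns only the tumor-negative type. Protocol 6.3 also has all collected SOC nodes imaged.

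**Conclusion.** Both parts hold.

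The localization definition contradicts the design sections on pathology confirmation, inside the primary endpoint and inside the SAP itself. How many subjects this affects cannot be known from the documents. It may be none, and it changes a subject's responder status only when that subject has no other CSE.

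The any-CSE rate alone does not show detection of disease that SOC missed, and the proportion of subjects with at least one tumor-finding CSE is not planned. With rows of 2, 2 and 2 of 40, that proportion is fixed only to between 5.0% and 15.0%. The share of the any-CSE rate due to tumor-negative specimens may be small or dominant, depending on specimen counts that the documents do not give. A reader might infer from the high case that the rate will be near 100%; the documents support no particular value.

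This is a gap in definition and presentation. It is not a calculation error, and it does not invalidate the composite.

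**What to change.** 1. Add pathology-confirmed disease to the localization definitions in SAP 5.1.1 and Protocol 9.3, so that they match SAP 3.1, the Protocol Summary and Protocol 3.1. This can change the composite count and should be acknowledged as such. SAP 7.1 allows updates before database lock and sends changes that may affect the primary conclusions to a protocol amendment; document the change on that basis.

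2. In SAP 7.10.1.1, beside the four-type rate, add the proportion of subjects with at least one synchronous-disease, positive-margin or pathology-confirmed NIR-localization CSE, with a Clopper-Pearson 95% interval. Use the same event definitions as the by-type rows, so that the bounds in step 2 hold. The SAP already records that Part 2 was not opened, so the row may come late in an open-label study: date it and label it supplementary and added late. Cite it together with the by-type rows for any statement about disease missed by SOC.

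The cost is one definition edit in each document and one table row. Fluorescence status and pathology are already collected per specimen, so no new data are needed. The downside for the sponsor is a less favorable detection figure beside the composite.
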